10.1.3. Procedure/Pre Hospital Discharge

Information collected at implant will include data from the day of the implant procedure and device testing including:

- Device information e.g. model, serial number, etc.
- Name of implanting physician
- General relevant procedure information: e.g. placement methods & location, technique
- Electrical measurements (pacing threshold, lead impedance, and sensing amplitude) submit device data e.g. uploads or transmissions. Report if measurements can't be reported due to subject condition (i.e. heart block, atrial fibrillation, etc.)
- Anticoagulation Strategies
- Implant Tools
- Fixation confirmation method

10.1.3.1. Unsuccessful Implant Detail

If a Micra device is not successfully implanted, subjects will be exited from the study within 30-days post the date of implant procedure unless a study system and/or implant procedure related Adverse Event (AE) is identified. If a study system and/or implant procedure related AE is identified, the subject will be followed until the event is resolved or no further actions need to be taken.

Confidential

10.1.4. Subject Follow-up

All subjects enrolled in the Micra Study will be prospectively followed from implant, 1 month, 3 months and 6 months, and at 6-month intervals thereafter through study closure. Subjects must be seen in-office for all follow-up visits. The study visits window is showing in Table 7.

Table 7: Study Visits Window

Visit	Visit Window
Implant	within 30 days after baseline
Pre-hospital discharge	within 7 days after implant
1-month	23 to 45 days after implant
3-month	77 to 105 days after implant
6-month	183 to 204 days after implant
12-month*	351 to 380 days after implant

**optional visit*

Information collected at post implant follow-up visits may include but is not limited to:

- Subject Status
 - Event assessment: confirmation of any new reportable Adverse Events/updates to previously reported Adverse Events
- Device Status:
 - Electrical measurements including pacing capture thresholds, impedance and sensing amplitude.
 - Assess device performance status through review of the device testing and interrogation. Confirm if there is any new reportable adverse device effect and/or treatment had been applied.
 - Adverse Events and update any unresolved previously reported events.

10.1.5. System Modification

A system modification will be reported if the Micra device requires an invasive procedure after the initial successful implant (e.g. explant, replacement, repositioning) or the Micra system is permanently electrically abandoned (i.e. programmed to OOO). If a new Micra device is implanted, this will be reported on a system modification eCRF as well as a new Implant procedure eCRF.

Following chronic placement of the Micra device, if an introducer sheath is introduced into the body to reposition, explant or replace the Micra system, this is considered a repeat intervention, which must be documented on a Micra System Modification eCRF(e.g. explant, repositioning or replacement).

Confidential

If a system modification requires explant of the entire Micra Study System, a complete system explant without replacement of any Study System components, the subject will be exited from the study. Subjects should not be exited from the study until all procedure, device related adverse events have been resolved or no further actions will be taken.

Information collected for a system modification procedure may include but is not limited to:

- General relevant modification procedure information (reason for modification, investigator, location of procedure, duration, access technique, etc.)
- Device information (model serial numbers, etc.)
- Electrical measurements
- Adverse Events assessment

Return any explanted Medtronic product to Medtronic for analysis and update the device disposition log for explanted investigational product. If the product(s) are explanted but not returned, a justification is required to be reported.

10.1.6. Electrical Measurement Requirements

Table 8 provides requirements meant to facilitate consistency in collection and reporting of electrical measurements.

Table 8: Electrical Measurement Requirements

	Implant	Pre-Discharge	Follow up
Impedance Measurement	x	x	x
R-Wave Measurement • If ventricular pacing is occurring on 1st measurement attempt, program to WI 40	x	x	x
Capture Management Threshold [contact]	x	x	x
Auto Decrement Threshold [contact]	x	x	x

10.2. Subject Consent

Informed consent is defined as legally effective, documented confirmation of a subject's (or their legally authorized representative or guardian) voluntary agreement to participate in the study. The Patient Informed Consent Form (ICF) is signed only after all relevant information regarding all aspects of the clinical study that are relevant to the subject's decision to participate throughout the clinical study has been provided to the subject. Subject consent will be obtained in accordance with local law and regulations. The ICF must be approved by the sponsor and the site's EC. The documents referenced must be maintained in such a way as to assure control of the document (i.e. version and/or date) such that the version(s) approved by the EC are clear with a documented change history for all revisions. The

Confidential

principal investigator or his/her authorized designee will conduct the informed consent process. Refer to Appendix E: Informed Consent Templates.

The process for obtaining informed consent shall:

- Avoid any coercion of, or undue influence of subjects to participate
- Not waive or appear to waive subject's legal rights
- Provide documents to the subject in a language s/he is able to read and understand
- Use language that is non-technical and understandable to the subject or legal representative
- Provide ample time for the subject to consider participation
- Include a dated signature of the subject or legal representative acknowledging their participation in the study is voluntary. Include personally dated signatures of the principal investigator or an authorized designee responsible for conducting the informed consent process.
- The informed consent shall be documented before any procedure specific to the clinical investigation is applied to the subject.

In the event that the subject can't read or write, a witnessed (impartial third party) consent form and authorization/data protection will be allowed (as determined by local law), provided detailed documentation of the process is recorded in the subject's case history and the witness signs and dates the appropriate consent form and authorization.

The signed ICF and the authorization must be filed at the site. A copy of the ICF must be provided to the subject. The original signed ICF and the authorization or other privacy language where required by law must be retained and made available for review by site monitors, auditors, or inspectors.

The consent process should be documented at each site in source documents which may include Medical charts, progress notes of medical history sheets, etc. Any changes to a previously approved Informed Consent Form throughout the course of the study must be approved by Medtronic and then by the Ethics Committee reviewing the application before being used to consent a prospective study subject. The document(s) must be controlled (i.e. versioned and/or dated, per local law) to ensure it is clear which version(s) were approved by the Ethics Committee. All important new information should be provided to new and existing subjects throughout the study, and if relevant, all affected subjects shall be asked to confirm their continuing informed consent in writing.

10.3. Assessment of Safety

Timely, accurate, and complete reporting and analysis of safety information is crucial for the protection of subjects, clinicians, and the sponsor. Reporting and analysis of safety data are mandated by regulatory authorities worldwide. Medtronic has established Standard Operating Procedures (SOPs) to ensure compliance with global regulatory safety reporting requirements. Study activities are conducted in accordance with these SOPs.

Procedure and device related adverse events are collected throughout the duration of this study, starting from the time of signing the CF through study closure. Adverse Events are to be reported upon site awareness using an event form, capturing date of the event; date site became aware of the event, diagnosis of the event, actions taken, assessment of seriousness, relatedness and outcome.

Confidential

Unavoidable Adverse Events (refer to Section 11.3) need not be reported unless the adverse event worsens or is present outside the stated timeframe

For AEs that require immediate reporting, initial reporting may be done on the CRF completing as much information as possible. The completed AE CRF must be sent to Medtronic as soon as possible.

Adverse Events will be recorded and reported according to local regulatory requirements and are outlined in Table 13. It is the responsibility of the Investigator to abide by the adverse event reporting requirements stipulated by local law and the sites' Ethics Committee.

10.4. Recording Data

Clinical data will be collected at baseline, implant/pre-hospital discharge, 1-month, 3-month, 6-month post-implant visits and at 6-month intervals thereafter if applicable through study closure. Data will be collected using electronic case report forms (eCRFs) using an electronic data management system for clinical studies. Data will be stored in a secure, password-protected database, which will be backed up nightly. Data will be reviewed using programmed and manual data checks. Data queries will be made available to study sites for resolution. Study management reports will be generated by Medtronic to monitor data quality and study progress. At the end of the study, the data will be frozen and retained indefinitely by Medtronic. Data collection requirements are summarized in Table 9.

Table 9: Summary of Data Collection and Frequency

	Enrollment/Baseline	Procedure/PHD	Follow-up*	Exit
Confirm Eligibility	X			
Consent	X			
Physical Exam, Demographics	X			
Medical History	X			
Procedure Details		X		
Anticoagulation Methods		X		
Device/System Information		X	X	X
Electrical Measurements & Device Interrogations		X	X	
Device Disposition				X
Adverse Events assessment		X	X	X

Confidential

	Enrollment/Baseline	Procedure/PHD	Follow-up*	Exit
Adverse Events		Upon Occurrence		
System Modification		Upon Occurrence		
Device Deficiency		Upon Occurrence		
Deaths		Upon Occurrence		
Protocol Deviations		Upon Occurrence		

* Follow up includes 1-month, 3-month, 6-month post-implant visits and at 6-month intervals thereafter through study closure if applicable.

10.5. Deviation Handling

A deviation is defined as an event within a study that did not occur according to the CIP or the Clinical Trial Agreement. Prior approval by Medtronic is expected in situations where the investigator anticipates, contemplates, or makes a conscious decision to deviate. Prior approval is not required when a deviation is necessary to protect the life or physical well-being of a subject in an emergency or in unforeseen situations beyond the investigator's control (e.g., subject failure to attend scheduled follow-up visits, inadvertent loss of data due to computer malfunction or inability to perform required procedures due to subject illness).

All study deviations must be reported on the Case Report Form regardless of whether medically justifiable, pre-approved by Medtronic, an inadvertent occurrence, or taken to protect the subject in an emergency. The description of the deviation and justification must be documented.

Once a deviation has been identified it should be reported to Medtronic as soon as possible. Deviations may be identified through numerous sources, including but not limited to: telephone conversations, site monitoring, subject record, or data review.

It is the site's responsibility to report deviations in compliance with their EC/IRB policies and/or local laws.

For medically justifiable conditions which preempt a subject's ability to complete a study-required procedure, it may be permitted to complete only one deviation which will apply to all visits going forward. This may also apply for other unforeseen situations (e.g., the subject permanently refuses to complete a study required procedure and the data will not contribute to the primary end point analysis). However, prior approval from Medtronic is required for such situations. (Example may include: unable to complete atrial threshold testing due to chronic AF, etc.).

In the occurrence of a corrupted device interrogation file, Medtronic may request a deviation to document that a readable interrogation file is unavailable. Deviations for missing device interrogation file(s) and missing or incomplete electrical testing at the same visit may be reported on one deviation CRF.

In the event the deviation involves a failure to obtain a subject's informed consent, or is made to protect the life or physical well-being of a subject in an emergency, the deviation must be reported to the IRB and Medtronic within five (5) working days. Reporting of all other study deviations should comply with IRB policies and/or local laws and must be reported to Medtronic as soon as possible upon the site becoming aware of the deviation. Reporting of deviations must comply with EC policies, local laws, and/or regulatory requirements.

Confidential

Medtronic is responsible for analyzing deviations, assessing their significance, and identifying any additional corrective and/or preventive actions (e.g., amend the CIP, conduct additional training, and terminate the investigation). Repetitive or serious investigator compliance issues may represent a need to initiate a corrective action plan with the investigator and site, and in some cases, necessitate suspending enrollment until the problem is resolved or ultimately terminating the investigator's participation in the study.

10.6. Subject Withdrawal or Discontinuation

Every attempt should be made to follow all Micra subjects through study closure.

Upon exiting from the study, no further study data will be collected or study visits will occur for the subject. All data available through the time of the subject's exit will be used for analysis.. In the event of study exit, the investigator should discuss with the subject the plans for future care and treatment. The investigator should explain that the subject will continue to receive standard medical care. Alternative treatment, such as medication options, implant of a commercially available system or follow-up through standard of care procedures instead of study procedures, and medical consequences should also be discussed. The investigator must notify the subject of any significant new findings that may become available during the course of the study, which are pertinent to the safety and well-being of the subject.

Exit

Subjects may be exited from the study for any of the following situations:

- Subject does not meet inclusion/exclusion criteria and was not implanted with investigational device of interest
- No implant attempted
- Implant attempted but was not implanted
- Explant of the investigational device with no planned replacement
- Lost to follow-up
- Subject chooses to withdraw from the study
- Investigator deems withdrawal necessary (medically justified or inclusion/exclusion criteria not met, failure of subject to maintain adequate study compliance)

In the event that a subject is exited from the study prior to study closure, all efforts should be made to continue following the subject until all unresolved procedure or device related adverse events are resolved or they are ongoing and no further actions will be taken.

It is recommended to perform a full device interrogation prior to the study exit. A copy of the interrogation files should be sent to Medtronic, with a copy also being maintained at the site.

Lost to Follow-up

In the case that the subject is determined to be lost to follow-up, details of a minimum of two attempts and the method of attempt (e.g., one letter and one phone record or two letters) to contact the subject must be recorded. In addition, the requirements set by the governing EC/IRB for subjects lost to follow-up must be followed.

Confidential

11. Risks and Benefits

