14.1.2.2. Rationale and Considerations for Sample Size Determination

The study size is determined by the sample size required for the primary objective. It is reported in the NEJM J2015⁷ that the Micra system and/or procedure related complication free survival probability through 6 months was 96%, (95% CI: 93.3%, 97.6%) in those who underwent Micra system implant

⁷Dwight Reynolds, Gabor Z. Duray , etc..A Leadless Intracardiac TranscatheterPacing System. N Engl JMed 2015;NEJMoa1511643:1-9.

Confidential

procedures. Therefore, we conservatively assume that the expected performance (or, "Success Rate" in later text) in the study population will be 94%. The OPC is set as 83% (the same performance threshold in the FDA approved global study). The sample size calculation assumes the statistical analysis will be carried out on 0.05 significance level, 2-sided, 80% power and 10% study attrition. The minimum sample size requirement is 82. The sample size formula is displayed as following:

$$n = \frac{[Z_{1-\alpha/2} \sqrt{p_0(1-p_0)} + Z_{1-\beta} \sqrt{p_T(1-p_T)}]^2}{(p_T - p_0)^2};$$

Where p_T is the expected success rate, p_0 is the OPC value, Z value is under normal distribution, α is the type I error (or significance level, 0.05 is used) and β is the type II error (0.2 is used to ensure 80% power).

The sample size calculation employed a formula based on the binomial distribution of the asymptotic normality method because the success rate estimate given by the Kaplan-Meier method is consistent with the actual observed success rate if there is no drop-outs.

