14.1.3. Significant Level and Statistical Power

For this study, the statistical significance level is set at 0.05 (two-sided), and the statistical power is specified at 80%.

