14.1.9. Criteria and Rationale for Selection of Subjects for Analysis

Statistical analysis sets should be clearly defined prior to the time when analysis is carried out. The analysis sets for this study are defined as follows:

Confidential

Full Analysis Set (FAS): This is a dataset defined per Intention-To-Treat principle, it refers to the set of all subjects who participates in the study and is exposed to the investigational device. In the event when data can't be collected from certain subjects, censoring or additional analysis may be applied..

Per Protocol Set (PPS): A subset of study subjects who complies to study protocol (The subject who has a violation related to study inclusion/exclusion criterion will be excluded from the PPS).

Safety Analysis Set (SS): The same definition as FAS should be used. Therefore, no additional definition is provided here.

The primary objective analysis will be performed on the FAS; all baseline demographic data and secondary objectives will be based on the FAS or PPS, and the safety assessment will be performed on the FAS. The electrical parameters will be analyzed on PPS.

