7.9.1.2 Statistical Analysis Method

All subjects who undergo an Micra implant procedure will be included in the analysis. The Kaplan-Meier survival analysis will be used to estimate the probability of a subject free from Micra TPS and/or procedure related relate major complications. The log-log transformation will be used to calculate the 95% confidence limits.

Definitions:

- Endpoint event for the survival analysis is Micra TPS and/or procedure related major complications, defined as those AEs resulting in:
 - Death
 - Permanent loss of device function due to mechanical or electrical dysfunction of the device (e.g. pacing function disabled, leaving device abandoned electrically)
 - System revision (reposition, replacement, explant)
 - Hospitalization
 - Prolonged Hospitalization by 48 hours or more

The CEC will determine if the AE is related to Micra TPS and/or procedure; and if the AE is a major complication. **Note:** Only system or procedure-related AEs will be classified as a major complication, minor complication or an observation. In the event the CEC provides an "Unknown" classification relationship to the Micra TPS and/or procedure, the event will not be considered "Related" for the primary endpoint analysis. Refer to section 7.9.1.4 for additional information.

- Censoring occurs in subjects who do not experience any Micra TPS and/or procedure related major complications
- Follow-up time: from the date of Micra implant procedure to
 - the onset date of a Micra TPS and/or procedure related major complication, or
 - study termination date (e.g. subject exit, die, or study closure, etc.), or
 - the date of Micra deactivation due to any reason that is not related to the Micra TPS or procedure (e.g. device system upgrade, the subject's other comorbidities, etc.), or
 - the last follow-up date, if none of the above occurs.

The statistical analysis of the primary objective will be 2-sided, using 0.05 significance level. The statistical analysis software package SAS will be used to conduct these analyses.

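### Protocol 10.6 allows an implanted subject to be exited for ineligibility, after which a new major complication before day 183 has no stated route into the primary analysis

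*Protocol*

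**What the plan says.** Protocol 10.6 opens by asking that every attempt be made to follow all Micra subjects to study closure. It then lists reasons for which a subject may be exited, two of which concern eligibility.

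- The first is limited by implant status: "Subject does not meet inclusion/exclusion criteria and was not implanted with investigational device of interest".
- The last is not: "Investigator deems withdrawal necessary (medically justified or inclusion/exclusion criteria not met, failure of subject to maintain adequate study compliance".

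On what follows an exit, the section says: "Upon exiting from the study, no further study data will be collected or study visits will occur for the subject". Its one qualification is that procedure- or device-related adverse events still unresolved at exit are followed to resolution, or until no further action will be taken.

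Protocol 14.1.9 defines the FAS by exposure: "it refers to the set of all subjects who participates in the study and is exposed to the investigational device". SAP 7.9.1.3 places the primary analysis on the FAS. In SAP 7.9.1.2 one of the dates that ends follow-up time is the "study termination date (e.g. subject exit, die, or study closure, etc.)", and the day count is the minimum of several dates that include study exit. Eligibility violations already have their own handling: a deviation report (Protocol 10.5) and the PPS rules (Protocol 14.1.9; SAP 7.1.3 and 7.1.4).

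**The concern.** The limit in the first exit reason is undone by the last. If monitoring finds an eligibility violation after implant, the investigator may end that subject's study follow-up while the device is in place. The primary endpoint counts related major complications to day 183. A new revision or related hospitalization after such an exit has no stated way to reach the CEC or the analysis.

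Kaplan-Meier estimation assumes that censored subjects carry the same remaining risk as those still followed. An exit at the investigator's discretion, made once the subject's course since implant is known, gives no assurance of that. For at least one exclusion (unstable angina or recent AMI) Protocol Table 6 itself cites greater susceptibility to complications. In a single-arm safety trial, events lost this way make the device look safer than it is.

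**Working it through.** **Inputs.** OPC p0 = 0.83, expected rate pT = 0.94, total N = 82 (Protocol 14.1.2.2); two-sided alpha 0.05 and power 80% (14.1.3); attrition 10% (14.1.4); horizon 183 days (6.2.1). The pass rule is a lower two-sided 95% log-log Kaplan-Meier limit above 83% (SAP 7.9.1.2).

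**1. The plan's own N.**
n = [1.960 × √(0.83 × 0.17) + 0.842 × √(0.94 × 0.06)]² / (0.94 − 0.83)²
= (0.7362 + 0.1999)² / 0.0121 = 0.8763 / 0.0121 = 72.42, rounded up to 73.
73 / 0.90 = 81.1, rounded up to 82. The stated figure is reproduced, and nothing below changes it.

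**2. Where the boundary lies.** With d failures among 82 and no earlier censoring, S = 1 − d/82, Greenwood sum G = d / [82 × (82 − d)], se = √G / |ln S|, and lower limit = S^exp(1.96 × se).

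- d = 6: S = 0.9268, G = 0.000963, se = 0.4083, limit = **84.4%** (pass).
- d = 7: S = 0.9146, G = 0.001138, se = 0.3781, limit = **82.9%** (fail).

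**3. Hidden failures needed to reverse a pass.** Assumed timing: observed failures on day 1; k implanted violators exited on day 30, each of whom would have failed on day 60.

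| Observed failures | k needed | Limit, exits censored | Limit, failures counted |
|---|---|---|---|
| 6 | 1 | 84.4% | 82.9% |
| 5 | 2 | 86.0% | 82.9% |
| 4 | 3 | 87.5% | 82.9% |
| 3 | 4 | 89.1% | 82.9% |

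For scale, expected failures are 82 × 0.06 = 4.9 at the planned 94%, and 82 × 0.04 = 3.3 at the global study's 96%.

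**4. Chance that the result is reversed.** The number of violators is not in the documents. Assume 1 to 4, all exited after the other subjects' failures have occurred, with every event of their own missed. For one violator at ordinary risk, a reversal needs exactly 6 failures among the other 81 plus one hidden failure: 0.146 × 0.06 = 0.9%. Over 1 to 4 violators:

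| Violators' risk | True rate 94% | True rate 96% |
|---|---|---|
| Same as others | 0.9% to 3.4% | 0.2% to 0.9% |
| Double | 1.8% to 7.0% | 0.5% to 2.0% |

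These are upper-end figures, because events before exit still count.

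**5. Average effect on S.** Assume 1 to 3 exits, each with a post-exit risk of 3% to 25%. Hidden events average 1 × 0.03 = 0.03 to 3 × 0.25 = 0.75. Divided by 82, S is overstated by about 0.04 to 0.9 percentage points. This too is an upper end: Kaplan-Meier already gives censored subjects the remaining risk of those still followed, so only the excess over that is bias.

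**The case against.** The case for leaving the text alone has substance.

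- **Exit is permissive, and the case is residual.** Subjects may be exited, not must be; the section opens by asking for full follow-up, and eligibility is to be confirmed before implant (Protocol 9.2 and 10.1.1). This stands as a limit on frequency. It does not reconcile the two exit reasons.
- **The FAS is not breached.** A reader might infer that such an exit removes the subject from the intention-to-treat set. It does not. The subject stays in the FAS, data before exit are used, and Protocol 14.1.9 allows for censoring where data cannot be collected. Only follow-up is cut short.
- **Missing data are not ignored.** SAP 7.9.1.4 describes an implanted subject who discontinues event-free and promises a summary of reasons; Protocol 14.4 and SAP 7.4 promise sensitivity analyses. But the worst-case and tipping-point analyses are tied to a true-missing condition. Its example is lost adverse-event data with an inconclusive CEC review, while SAP 7.1.4 item 3 uses the term for any subject whose primary endpoint cannot be obtained. Whether an investigator-initiated exit qualifies is unclear.
- **Higher risk is not general.** A reader might infer that ineligible subjects as a group are at higher risk, so that bias is certain. The susceptibility rationale belongs to one of 14 exclusions. Others concern telemetry range, co-enrollment or local law.
- **Late events may be few.** In Protocol Table 1, 16 of the 28 major complications in the global study (11 cardiac injury, 5 groin site) are of types linked to the implant procedure, and device dislocation occurred once in 725 subjects. The table gives no timing, so this is suggestive only.

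**Conclusion.** The inconsistency in Protocol 10.6 is real, and each step to its consequence is in the text: permission to exit an implanted ineligible subject, no new data after exit, censoring at the exit date. What is lost is a new related major complication between exit and day 183. Events before exit, and related events unresolved at exit, are still covered.

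The effect is probably small. It is below about 1 percentage point on the 6-month rate over the ranges assumed, and it can reverse the conclusion only near the boundary between 6 and 7 failures. The number of exits, their timing and the post-exit risk are all assumptions. The documents do not support a claim that the primary result is likely to be wrong, nor that the bias must favour the device in every case. The poor-compliance ground in the same exit reason also reaches implanted subjects, but nothing in the documents ties it to risk, so it is secondary. The point merits a change because the discretion serves no analytic purpose and is cheap to remove.

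**What to change.** **Protocol 10.6.** In the last exit reason, limit the eligibility ground to subjects without an implanted Micra. Add that an eligibility violation found after implant is recorded as a deviation, is handled through the PPS, and does not end endpoint follow-up before the 6-month visit. Leave subject-initiated and medically justified withdrawal as they are.

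**SAP 7.9.1.4.** State that, for that section, an investigator-initiated exit before day 183 without a primary endpoint event counts as true missing, so that the worst-case and tipping-point analyses are run.

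**Cost.** A few subjects complete visits already in the schedule, and one small sensitivity analysis is added. The sample size of 82 is unaffected.
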